5 STUDY DESIGN

5.1 Overall Design

This is a multicenter, placebo-controlled, Phase 2 study with a double-blind, randomized, 2:1 group design in Japanese participants with de novo AML or AML secondary to prior diagnosis of MDS or CMML, aged ≥ 55 years, who are in first CR/CRi following induction therapy with or without consolidation chemotherapy.

The study consists of 3 phases; the Screening Phase, the Treatment Phase, and the Follow-up Phase. The study design schematic is presented in [Figure 5.1-1](#).

Approximately 15 participants will be randomized 2:1 to CC-486 or placebo.

- Approximately 10 participants will receive CC-486.
- Approximately 5 participants will receive placebo.

After informed consent is obtained, participants will undergo screening procedures to determine eligibility (28 days for screening). Eligible participants will be dynamically randomized using an Interactive Response Technology (IRT) by the following factors:

1. Age: 55 to 64 years/ \geq 65 years
2. Prior history of MDS/CMML: Yes/No
3. Cytogenetic risk: Intermediate/Poor
4. Consolidation therapy: Yes/No

Randomization must occur within 4 months (\pm 7 days) of achieving the first CR/CRI.

After randomization, no crossover between the treatment arms will be permitted at any point during the study. During the Double-blind Treatment Phase, participants will ingest Investigational Product (IP) (CC-486 tablets or placebo tablets) for the first 14 days of each 28-day cycle. Dose modifications may occur for managing toxicity if necessary during treatment ([Section 7.4.1](#)).

During the Double-blind Treatment Phase, participants will be assessed for safety, tolerability, and efficacy. Assessments during the Double-blind Treatment Phase will include monitoring for AEs, monitoring for relapse of AML, physical examination, vital signs and weight measurement, Eastern Cooperative Oncology Group (ECOG) performance status, hematology and serum chemistry, pregnancy testing (women of childbearing potential [WOCBP] only), concomitant medications, therapies and procedures, review of bone marrow aspirate (or biopsy if adequate aspirate is not attainable) and peripheral blood smear slides, cytogenetic analysis, CR/CRI status assessment, bone marrow and peripheral blood sampling for biomarker analysis, blood sampling for PK analysis, IP administration and accountability, and HRQoL.

A separate central review of all bone marrow aspirates, bone marrow biopsies, and peripheral blood smears will be conducted by a pathologist blinded to participant treatment. The central reviewer's assessments will be used to confirm the CR/CRI status at screening and during treatment for maintenance assessment. If the central reviewer and local pathologist disagree on the CR/CRI status of a participant, a third-party reviewer will adjudicate and make the final assessment.

The central cytogenetic review will provide standardized analysis and reporting for all participants, regardless of the laboratory performing the initial analysis (local or central).

[figure not shown]
In participants on study who have subsequent evidence of AML relapse with blasts \geq 5%, either in the peripheral blood or bone marrow, and provided the blasts are no greater than 15% in the blood or bone marrow, escalation of the dosing regimen (dose and/or schedule) can be implemented ([Section 7.4.2](#)).

Participants will be discontinued from treatment when they meet the following criteria:

- Appearance of > 15% blasts in the bone marrow or peripheral blood.
- The above occurrence should be attributed to relapse following CR/CRI and not attributable to any other cause (eg, bone marrow regeneration after consolidation therapy).

All discontinued participants, regardless of reason for discontinuation, should undergo Treatment Discontinuation Visit procedures at the time of study discontinuation. Participants will have a follow-up visit for the collection of AEs up to 28 days after last dose of IP or up to the Treatment Discontinuation Visit, whichever is longer. After this follow-up visit, participants will be followed for survival every month for the first year and then every 3 months until death, withdrawal of consent for further follow-up, until a participant is lost to follow-up or study end, or when the commercial product of CC-486 becomes available at the site, whichever comes first.

Figure 5.1-1: Study Design Schema

^aIWG 2003; assessment for CR/CRI or relapse at the Cycle 3; if CC-486 treatment continues, response assessed every 3rd cycle (ie, Cycles 6, 9, 12, etc).
^bFor participants receiving the initially assigned dose level and schedule.

alloSCT, allogeneic stem cell transplantation; AML, acute myeloid leukemia; APL, acute promyelocytic leukemia; BM, bone marrow; BSC, best supportive care;

CAML, chronic myelomonocytic leukemia; CR, complete remission; Cri, complete remission with incomplete blood count recovery;

ECOG PS, Eastern Cooperative Oncology Group performance status; HMA, hypomethylating agent; IWG, International Working Group; MDS, myelodysplastic syndrome; OS, overall survival; PBO, placebo; QD, once daily

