- Candidate for allogeneic bone marrow or stem cell transplant at screening.
- Have achieved CR/CRI following therapy with hypomethylating agents
- Received therapy with hypomethylating agents for MDS and went on to develop AML within four months of discontinuing the therapy with hypomethylating agents.

Intervention Groups and Duration:

Total duration of study participation for each participant: screening phase for 4 weeks, treatment phase until AML relapse, and follow-up phase until death, withdrawal of consent, study termination, or loss to follow-up.

Dose regimen: 200 mg once daily of CC-486 or placebo will be taken for the first 14 days of each 28-day treatment cycle.

Dose modification for toxicity and dose/schedule adjustment with AML relapse are allowed.

Study Intervention:

Study Intervention for CA055005		
Medication	Potency	IP/Non-IP/AxMP
CC-486	150mg/200mg	IP
Placebo	150mg/200mg	IP

Abbreviations: AxMP, auxiliary medicinal product; IP, Investigational Product.

Statistical Methods:

The primary efficacy analysis will be conducted for the Intent-to-Treat Population and will compare the RFS distributions between the two treatment groups. A Cox proportional hazards model will be used to estimate the corresponding hazard ratio and 95% CI for CC-486 relative to placebo. The RFS curves will be estimated using Kaplan-Meier methods.

Data Monitoring Committee: No

A Data Monitoring Committee or other review committee will not be used in the study.

Other Committee: No

Other review committee will not be used in the study.

Brief Summary:

CA055-005 is designed as a 2:1 randomization of CC-486 or placebo to assess the efficacy and safety of maintenance treatment with oral azacitidine in a cohort of Japanese participants ≥ 55 years with AML, and in CR/CRi after intensive induction chemotherapy with or without consolidation chemotherapy. The primary endpoint of RFS and the secondary endpoints of OS, safety, PK, and HRQoL will be evaluated and allow for a comprehensive investigation of efficacy, exposure/safety, and appropriateness of the clinical recommended dose for the Japanese population in comparison with the data from Study CC-486-AML-001.

Study Duration: 3 years

Study Intervention Duration: Until AML relapse in each participant.

Study Visit Frequency: On Days 1, 8, 15 and 22 in Cycles 1 and 2, Days 1 and 15 in Cycles 3 through 24, and Day 1 in Cycle 25 and beyond.

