Follow-up AML Therapies		X	All discontinued participants, regardless of reason for discontinuation, should be followed for AML therapies every 4 weeks (\pm 3 days) for the first year and then every 12 weeks (\pm 14 days) until death, loss to follow-up, withdrawal of consent from further follow-up, or end of study.

Table 2-3: End-of-treatment and Follow-up Procedural Outline (CA055005)

Procedure	End of Treatment /Early Termination	Follow-up	Notes
Survival Follow-up		X	All discontinued participants, regardless of reason for discontinuation, should be followed for survival every 4 weeks (\pm 3 days) for the first year and then every 12 weeks (\pm 14 days) until death, lost to follow-up, withdrawal of consent from further follow-up, or the end of the study. The survival follow-up can be performed via a telephone interview.
Health Outcomes Assessments			
FACIT-Fatigue Scale and EQ-5D-5L	X		Each assessment should be completed at the start of the clinic visit prior to dosing and other study assessments. See Section 9.1.2 .

Abbreviations: ALT, alanine aminotransferase; AML, acute myeloid leukemia; ANC, absolute neutrophil count; AST, aspartate aminotransferase; BUN, blood urea nitrogen; COVID-19, coronavirus disease 2019; CR, complete remission; CRF, case report form; CRi, complete remission with incomplete blood count recovery; EOT, end of treatment; EQ-5D-5L, EuroQol 5-dimension 5-level questionnaire; FACIT, Functional Assessment of Chronic Illness Therapy; IgG, immunoglobulin G; IgM, immunoglobulin M; IP, Investigational Product; IWG, International Working Group; LDH, lactate dehydrogenase; MCH, mean corpuscular hemoglobin; MCHC, mean corpuscular hemoglobin concentration; MCV, mean corpuscular volume; RBC, red blood cell; SAE, serious adverse event; WBC, white blood cell; WOCBP, women of childbearing potential.

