All participants who discontinue study intervention should comply with protocol-specified follow-up procedures as outlined in [Section 2](#). The only exception to this requirement is when a participant withdraws consent for all study procedures, including post-treatment study follow-up, or loses the ability to consent freely (eg, is imprisoned or involuntarily incarcerated for the treatment of either a psychiatric or physical illness). Additionally, all participants who are discontinued from protocol-prescribed treatment will be followed for a period of 28 days following

the last dose of IP or until the date of the last study visit, whichever is later, for the collection of AEs. Discontinued participants will not be replaced.

If study intervention is discontinued prior to the participant's completion of the study, the reason for the discontinuation must be documented in the participant's medical records per local regulatory requirements in each region/country and entered on the appropriate CRF page.

8.1.1 *Post-study Intervention Study Follow-up*

In this study, RFS is the primary endpoint of the study. Post-study follow-up is of critical importance and is essential to preserving participant safety and the integrity of the study. Participants who discontinue study intervention must continue to be followed (in this study or a rollover study) for collection of outcome and/or survival follow-up data as required and in line with [Section 5](#) until death or the conclusion of the study.

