9.1 Efficacy Assessments

9.1.1 Efficacy Assessment for the Study

International Working Group Response

International Working Group (IWG) response assessment will be assessed at Cycles 3, 6, 9, 12, 15, 18, 21, 24, 30, 36, and the Treatment Discontinuation Visit. After Cycle 36, IWG response assessment will be performed if clinically indicated at the discretion of the Investigator. Participants should be assessed for CR/CRI status maintenance or disease relapse.

Bone Marrow Aspirate, Biopsy, and Peripheral Blood Smear

Bone marrow aspirate (or biopsy if adequate aspirate is not attainable) samples during the Double-blind Treatment Phase should be collected at Screening, on Day 1 (\pm 7 days) of Cycles 3, 6, 9, 12, 15, 18, 21, 24, 30, 36, and the Treatment Discontinuation Visit. After Cycle 36, bone marrow aspirate collection and evaluation will occur if clinically indicated at the discretion of the Investigator.

Additional bone marrow samples should be collected as clinically indicated. A bone marrow biopsy must be collected if adequate aspirate is not attainable. Whenever a bone marrow sample is collected, a peripheral blood smear is to be prepared.

Instructions for submission of bone marrow samples are provided in Study Reference Manual and/or Study Central Laboratory Manual.

Cytogenetics

Bone marrow cytogenetic testing is to be completed whenever a bone marrow aspirate (or biopsy if adequate aspirate is not attainable; note that specific handling of the biopsy is required if it is to be used for cytogenetics testing [refer to the Laboratory Manual for sample collection, handling, and processing instructions]).

Follow-up AML Therapies

All discontinued participants, regardless of reason for discontinuation, should be followed for subsequent AML therapies every month for the first year and every 3 months thereafter until death, loss to follow-up, withdrawal of consent from further follow-up, or study closure. Subsequent AML therapy follow-up can be performed via the telephone.

Survival Follow-up

All discontinued participants, regardless of reason for discontinuation, should be followed for survival every month for the first year and every 3 months thereafter until death, loss to follow-up, withdrawal of consent from further follow-up, or study closure. The survival follow-up can be performed via telephone.

9.1.2 *Health-related Quality of Life*

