10.4.3 Secondary Endpoint(s)

Overall Survival

The secondary efficacy endpoint of OS is defined as the time from randomization to death from any cause and will be calculated using the randomization date and date of death, or date of last follow-up for censored participants. All participants will be followed until dropout, death, or study termination. Participants who dropout or are alive at study termination will have their OS times censored at the time of last contact, as appropriate. OS analysis will be conducted for the ITT population.

Safety

All safety analyses will be performed on the Safety Population. Adverse events will be coded using the Medical Dictionary for Regulatory Activities (MedDRA). Adverse event listings will include the verbatim term and the MedDRA preferred term. Treatment-emergent adverse events (TEAEs) will be summarized by worst severity grade, system organ class, and preferred term. Treatment-emergent AEs leading to death or to discontinuation from treatment, AEs classified as NCI-CTCAE (Version 5.0) Grade 3 or Grade 4, AEs related to IP, and SAEs will be summarized separately. Time to discontinuation from the study due to AE will be summarized using KM methods. Listings of all deaths and all SAEs, regardless of when they occurred, will also be generated.

Pharmacokinetics

The sparse concentration-time data collected in this study may be combined with a larger dataset to help further develop and validate the population pharmacokinetic model for azacitidine and to aid in the identification of covariates that influence azacitidine pharmacokinetic and/or pharmacodynamic measures and efficacy and safety endpoints. PK population will be used for PK analysis. Noncompartmental analysis will be performed using intensive sampling data.

Health-related Quality of Life

PRO endpoints include FACIT-Fatigue and the EQ-5D-5L, and analyses will include the Health-related Quality of Life population. Summary statistics (N, mean with SD and 95% CI, median, first and third quartiles, minimum, maximum) for PRO measures at each assessment point will be provided for each treatment arm. The mean change from baseline will also be reported at each post-baseline assessment point. Additionally, for the EQ-5D-5L, the proportion of participants endorsing each response option will be calculated at each time point.

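### Section 5.1 stops survival follow-up of off-treatment participants when commercial CC-486 reaches the site; four other sections do not, and followed literally the rule can inflate OS

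*Combined protocol and SAP*

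**What the plan says.** Section 5.1 describes what happens once treatment has stopped and the post-treatment adverse event visit is done: "After this follow-up visit, participants will be followed for survival every month for the first year and then every 3 months until death". The list of end points then continues through withdrawal, loss to follow-up and study end, and closes with "or when the commercial product of CC-486 becomes available at the site, whichever comes first". Study end is a separate item in that list, so commercial availability cannot be read as another name for it.

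The other descriptions of the same follow-up are:

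- Protocol Summary: "follow-up phase until death, withdrawal of consent, study termination, or loss to follow-up".
- Table 2-3, Survival Follow-up row: "until death, lost to follow-up, withdrawal of consent from further follow-up, or the end of the study".
- Section 9.1.1, Survival Follow-up: "every 3 months thereafter until death, loss to follow-up, withdrawal of consent from further follow-up, or study closure".
- Section 10.4.3, Overall Survival: "All participants will be followed until dropout, death, or study termination". OS is censored at last contact, and the availability trigger is not mentioned.
- Section 8.1.1: "until death or the conclusion of the study". The same sentence ties the follow-up to Section 5, so it carries the conflict rather than adding an independent contradiction.

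**The concern.** A site cannot comply with both versions. If availability comes first, following Section 5.1 means stopping contacts that Table 2-3 and Section 9.1.1 require.

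The statistical issue is who gets censored. The clause covers only people already off treatment. The disease criterion for stopping in Section 5.1 is "Appearance of > 15% blasts in the bone marrow or peripheral blood" attributed to relapse, and Section 3.1 puts median survival after relapse at 3 to 12 months. No section sends on-treatment participants out of follow-up on the same date. Read literally, censoring therefore depends on a post-randomisation state that predicts death, and Kaplan-Meier and Cox analyses of OS assume that it does not.

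OS is secondary and untested. Even so, Table 3.3.1-1 says the bridging judgement will weigh secondary endpoints as well as RFS for consistency with Study CC-486-AML-001. With about 15 participants, each lost death counts.

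**Working it through.** **Plan's own figure.** The plan states no figure for OS. Its one design figure, the 87% in Section 10.2, concerns RFS and does not bear on this point. It does confirm the planning inputs. With HR = 4.8/9.5 = 0.505, 2:1 allocation and 24 months' uniform accrual plus 12 months' follow-up, about 12.8 events are expected. Then P(estimated HR < 1) = Φ(|ln 0.505| × √(12.8 × 2/9)) = Φ(0.683 × 1.69) ≈ 87.5%.

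**Inputs from the documents.**
- 15 participants, 10 vs 5 (5.1).
- RFS medians 9.5 and 4.8 months (10.1).
- Study duration 3 years (Protocol Summary) and primary analysis 12 months after the last participant (10.1), which together suggest about 24 months' accrual and a cut-off at month 36.
- Post-relapse median survival 3 to 12 months (3.1).

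**Assumptions.**
- Exponential times; 10% of RFS events are deaths.
- Post-relapse median 6 months, with 10 as an alternative.
- Treatment stops at relapse.
- On-treatment participants stay under observation throughout.
- Availability at month 24.

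**True 24-month OS under this model.** With a = ln 2/RFS median and b = ln 2/post-relapse median,
S(t) = e^(−at) + 0.9 × [a/(b − a)] × (e^(−at) − e^(−bt)).
For CC-486, a = 0.0730 and b = 0.1155, so S(24) = 0.174 + 0.9 × 1.714 × (0.174 − 0.0625) ≈ 0.345.

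**Three follow-up rules compared by large simulation.** Under the Section 5.1 rule, off-treatment participants are censored at availability, and those who stop later are censored 28 days after stopping.

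| Rule (availability month 24, 6-month post-relapse median) | Expected deaths of 15 | CC-486 24-month OS | OS HR |
|---|---|---|---|
| Follow-up to study end | 10.3 | 0.35 | 0.59 |
| Section 5.1 read literally | 6.3 | 0.49–0.50 | 0.54–0.55 |
| Everyone cut at month 24 | 5.5 | 0.34 | 0.58 |

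The common cut loses slightly more deaths than the literal rule but leaves OS where it should be. The inflation therefore comes from selective censoring, not from shorter follow-up.

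**Sensitivity.**
- Post-relapse median 10 months: deaths 8.6 to 5.0, CC-486 24-month OS 0.46 to 0.59.
- Availability at month 18 (6-month median): deaths 10.3 to about 4.5. At month 30: 10.3 to 8.4.
- Availability after month 36: no change.

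**Second calibration**, to the medians in Section 3.2 (RFS 10.2 and 4.8 months, OS 24.7 and 14.8 months; all RFS events taken as relapses):

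| Rule | Expected deaths of 15 | 24-month OS, CC-486 vs placebo | OS HR |
|---|---|---|---|
| Follow-up to study end | 8.3 | 0.51 vs 0.25 | 0.47 |
| Section 5.1, month 24 | 4.2 | 0.67 vs 0.36 | 0.40 |
| Section 5.1, month 30 | 6.3 | 0.57 vs 0.27 | 0.43 |
| Section 5.1, month 33 | 7.4 | 0.54 vs 0.26 | 0.45 |
| Everyone cut at month 24 | 4.0 | 0.52 vs 0.25 | 0.45 |

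Both arms are inflated. Here part of the HR movement (0.47 to 0.45) also occurs under the common cut.

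**Size against precision.** With 10.3 deaths, SE(log HR) ≈ 1/√(10.3 × 2/9) = 0.66, so an HR of 0.59 has a 95% CI of about 0.16 to 2.2. The move to 0.54 is ln(0.59/0.54)/0.66 ≈ 0.13 SE. The move in the OS rate is larger in these terms: for 10 CC-486 participants a binomial SE is √(0.345 × 0.655/10) = 0.15, about equal to the inflation itself.

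**The case against.** The strongest reply is that the bias is conditional. The documents give no availability date. This is a bridging study meant to support extrapolation to Japan, so marketing could well follow its results, although the documents do not say so. If availability comes after the OS cut-off, the clause does nothing. Nor do the documents say what happens to on-treatment participants at availability. If everyone at a site left that day, censoring would be administrative, and only events would be lost. Both conditions stand and belong in the statement of the point. Section 7.8 does not settle the second: it deals with drug supply at the conclusion of the study, not with a common exit date.

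The model is also simple. Section 8.1 allows stopping for adverse events, participant request or transplant eligibility, so off treatment does not always mean relapsed. Section 7.4.2 lets participants with 5% to 15% blasts remain on treatment. The 6-month case gives a CC-486 24-month OS of 0.35, below what the 24.7-month median in Section 3.2 implies; the second calibration removes that mismatch and shows the same direction.

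Three stronger readings are tempting but unsupported:

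- That Section 8.1.1 is a further independent contradiction. It refers back to Section 5.
- That the clause can shorten the 12-month follow-up behind the primary analysis. Section 10.1 times the RFS analysis, and the relapse follow-up row of Table 2-3 has no availability stop.
- That the OS hazard ratio would shift visibly towards CC-486. The shift is far inside its uncertainty, part of it can come from shorter follow-up, and Section 10.4 already warns that some estimates may not be meaningful at this size.

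**Conclusion.** The contradiction is in the current text and holds without any assumption: Section 5.1 conflicts with the Protocol Summary, Table 2-3, Section 9.1.1 and Section 10.4.3.

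The effect on OS is conditional. If availability precedes the OS cut-off and on-treatment participants remain under observation, the literal rule loses deaths and biases Kaplan-Meier OS upwards in both arms. In the illustrations with availability at month 24, about four deaths are lost and CC-486 24-month OS rises by about 0.13 to 0.16. The effect shrinks with later availability and vanishes after the cut-off. These sizes rest on an assumed date and model; they show direction and order of magnitude, not a forecast. Primary RFS is not directly affected. The point should be corrected because it concerns a secondary endpoint used in the bridging comparison and the remedy is nearly free.

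**What to change.** Preferred: delete the commercial-availability clause from survival follow-up in Section 5.1, so that it matches the Protocol Summary, Table 2-3, Section 9.1.1 and Section 10.4.3. Section 8.1.1 then needs no change.

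Alternative, if the sponsor wants the study to end at availability: set one calendar data cut for every participant, on or off treatment, write it into all these sections, and state the resulting OS censoring date in Section 10.4.3.

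Cost: a wording change. The first option adds at most some survival contacts in about 15 participants, which Section 9.1.1 already allows by telephone. The second adds no contacts but yields fewer observed deaths (about 5.5 instead of 10.3 in the month-24 illustration).
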